COVER PAGE

Document Type:

STUDY PROTOCOL

Official study title:

Computational Design, Fabrication, and Evaluation of Optimized Patient-Specific Transtibial Prosthetic Sockets

NCT number:

not yet assigned

Document Date:

02/15/2018

Principal investigator:

[name]

Sponsor:

NIH

Participating sites:

Massachusetts Institute of Technology (MIT), Cambridge, MA, USA
McGovern Institute for Brain Research, MIT, Cambridge, MA, USA

STUDY PROTOCOL

I. BACKGROUND AND RATIONALE

The overall goal of this study is to further develop, and clinically assess, a computational and data-driven design and manufacturing framework for mechanical interfaces that quantitatively produces transtibial prosthetic sockets in a faster and more cost-effective way compared with conventional processes.

In the United States, 623,000 people live with major lower extremity loss, with that population expected to double by 2050 [1]. The U.S. Department of Veterans Affairs estimates lower extremity amputation (LEA) to account for more than \$250 million in direct expenditures each year, not including civilian cases [2]. Complications of prosthetic leg use in persons with LEA often occur at the prosthetic socket, and includes delayed wound healing, recurrent skin ulcerations, and pressure damage to soft tissues [3]–[6]. Such complications can result in limited mobility, which further contributes to conditions such as obesity, musculoskeletal pathologies, and cardiovascular disease [7]–[9]. Conventional prosthetic socket fabrication is an artisanal process requiring substantial human hours, financial cost and patient involvement for evaluation. Computer aided design (CAD) (e.g.[10]–[13]) and computer aided manufacturing (CAM) (e.g.[14]–[24]) methods have been explored as an alternative. However, these tools have not reached full clinical efficacy and do not inform the design in a data-driven sense since the actual design process remains a manual and experience-based procedure [25]. The long-term goal of our research is to develop a fully-quantitative process for prosthetic socket design and production that requires minimal patient involvement and can be delivered at affordable price points.

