In pursuit of our long-term goal, our team has recently developed a framework for prosthetic socket design and fabrication [26] that involves: 1) non-invasive imaging to record patient geometry, 2) indentation to assess tissue mechanical properties, 3) data-driven and automated creation of patient-specific designs, 4) patient-specific finite element analysis (FEA) and design evaluation, and 5) 3D printing of the end design for clinical evaluation.

II. OBJECTIVES

The overall goal of this study is to further develop and clinically assess a computational and data-driven design and manufacturing framework for mechanical interfaces that quantitatively produces transtibial prosthetic sockets in a faster and more cost-effective way than conventional processes. Traditionally, prosthetic socket production has been a craft activity, based primarily on the experience of the prosthetist. Even with advances in computer-aided design and computer-aided manufacturing (CAD/CAM), the design process remains manual. The manual nature of the process means it is non-repeatable and currently largely non-data-driven, and quantitative data is either not obtained or insufficiently employed. Furthermore, discomfort, skin problems and pressure ulcer formation remain prevalent. Through the proposed computational modeling framework, a repeatable, data-driven and patient-specific design process is made available which is based on scientific rationale.

Objective/hypothesis: The main hypothesis of this proposal is that a socket, designed using the novel computational design framework, is equivalent to, or better than, a conventional socket (designed by a prosthetist) in terms of: 1) skin contact pressures, 2) gait symmetry, 3) walking metabolic cost, 4) skin irritation levels as assessed by the dermatologist, and 5) comfort as evaluated from a questionnaire. Our hypothesis is supported by the presented pilot data which shows reduced or equivalent skin contact pressures and subject reported comfort levels for several critical anatomical regions.

Specific Aims: 1) Subject-specific biomechanical modeling for N=18 subjects, 2) Computational design and fabrication of sockets for N=18 subjects, and 3) Clinical evaluation of novel sockets for N=18 subjects.

III. STUDY POPULATION

Sample Size

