18 healthy participants with below-knee amputations will be recruited. Participants will be generally healthy and will have no other musculoskeletal problems or any known cardiovascular, pulmonary or neurological disorders. This study will consider subjects of all sex/gender, race, and/or ethnic orientation, provided that they conform to the inclusion criteria summarized below. We focus on healthy subjects who are unilateral or bilateral transtibial amputees, who are between 18-64 years old, have an activity level of at least K3 (a person with the ability or potential for ambulation with variable cadence, and to traverse most environmental barriers and may have vocational, therapeutic or exercise activity that demands prosthetic use beyond simple locomotion.) and that their amputation took place more than 1 year prior to the start of the study. The latter is to exclude subjects whose limbs will undergo significant changes during the course of the study. Another inclusion criterion relates to the subject's prosthetic sockets. In this study a comparison is made between a subject's conventional sockets (designed by their experiences prosthetist) and our novel (computational modeling derived) sockets. Since we aim to match or improve upon comfortable prosthetic sockets, we will only include subjects whose current conventional sockets are deemed comfortable and of high quality. The quality of a subject's conventional sockets will be judged by the consultant and certified prosthetist involved in this study ([name], A Step Ahead Prosthetics). One further inclusion criterion relates the subject's ability to undergo MRI. If subjects are unable to

undergo MRI (e.g. due to claustrophobia or the presence of objects their body that are not MRI Safe) they are excluded from this study.

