In order to address the hypothesis that the novel sockets can perform equivalently to, or better than, conventional sockets (designed by a qualified prosthetist) we propose an experimental evaluation using N=18 subjects. Static standing and walking exercises will be performed. During the standing and walking exercise skin contact pressures will be recorded. During walking skin contact pressure, metabolic cost, and motion capture data will be recorded. Finally, a custom socket evaluation questionnaire will be used to assess the level of socket comfort experienced by the subject.

This study consists of three phases:

- 1) Data collection
- 2) Socket design
- 3) Socket evaluation

Participant involvement is required for phase 1 and 3 which occur in two separate sessions.

Session 1 (phase 1): Data collection

In the first session, each amputee participant will be scheduled to visit the Biomechatronics Group in The MIT Media Laboratory and our imaging center (the MIT McGovern Institute). The main purpose of this session is to quantitatively measure the stiffness of the residual limb and map out the anatomy of the residual limb, for N=18 subjects, by using Magnetic Resonance Imaging (MRI), 3D scanner, ultrasound scanner, and a stiffness-measuring device on the amputee. Mechanical property investigation may also take place during imaging, e.g. during MRI by using MRI compatible indenter systems. Subjects are scanned using a 3T MRI system (Siemens Magnetom 3 Tesla, Siemens Medical Systems, Erlangen, Germany). The structural and geometrical data derived from MRI (e.g. using segmentation) provides the input for computational model development (used in the socket design process). Morphological data (such as height, weight, limb length and circumference) of the participant will also be recorded.

Session 2 (phase 3): Socket evaluation.

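### No entry rule or baseline check covers residual-limb skin, so existing irritation cannot be told apart from irritation caused by the socket just worn

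*Protocol*

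**What the plan says.** **Why skin matters to this trial.** Protocol section I lists among socket complications "delayed wound healing, recurrent skin ulcerations, and pressure damage to soft tissues". Section II states that "discomfort, skin problems and pressure ulcer formation remain prevalent", and ends its list of hypothesis components with "4) skin irritation levels as assessed by the dermatologist, and 5) comfort as evaluated from a questionnaire".

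**Who may enter.** In section III, under Inclusion and exclusion criteria, the health requirement is "Participants will be generally healthy and will have no other musculoskeletal problems or any known cardiovascular, pulmonary or neurological disorders". The other criteria concern age, amputation level, activity level, time since amputation, the current socket and MRI. On the socket, "we will only include subjects whose current conventional sockets are deemed comfortable and of high quality", and "The quality of a subject's conventional sockets will be judged by the consultant and certified prosthetist involved in this study". For the rule of more than one year since amputation, the stated reason is "The latter is to exclude subjects whose limbs will undergo significant changes during the course of the study". Skin, wounds and ulcers are not mentioned.

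**What is done to the limb.** The Session 1 instruments include "ultrasound scanner, and a stiffness-measuring device on the amputee". In Session 2 sensors are taped to the skin, and each socket is worn for 5 minutes of standing and 10 minutes of treadmill walking.

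**When the skin is examined.** Section V places the dermatologist's inspection after the exercises, with one report following each socket test. No inspection is described before Session 1, before the first socket, or as a starting record for the second.

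**The concern.** The protocol treats skin breakdown as a known problem in this population and makes irritation an outcome, but it neither screens for skin problems nor records the starting state. Two things are at stake.

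- **Safety.** The Risks section calls the non-MRI risks minimal because they are those of standing and treadmill walking, and plans no follow-up on the ground that injury is unlikely. It does not discuss indentation or adhesive tape on a limb that is already damaged. That reasoning presumes sound skin, and no entry rule secures it.
- **Attribution.** The hypothesis concerns irritation as an effect of the socket. A report written only after wear describes the state of the skin, not what the socket did to it. Without a starting record, an old lesion and a new one can look alike.

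**Working it through.** No stated figure underlies the skin component: the documents give no lesion prevalence, irritation scale, SD or test for it. The check is therefore mainly a reading of the text, with three small calculations.

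**1. Does any existing rule or safeguard cover residual-limb skin?**

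| Rule or safeguard | What it covers | Does it cover residual-limb skin? |
|---|---|---|
| General health and named organ systems | Musculoskeletal, cardiovascular, pulmonary, neurological | Not named |
| Comfortable, good-quality current socket | The socket, judged by the prosthetist | Indirectly |
| More than 1 year since amputation | Limb change during the study | Not named |
| Prosthetist and dermatologist present | Fitting and evaluation in Session 2 | No recorded pre-test inspection; does not reach Session 1 |

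**2. What can the post-wear reports show?** Assume a graded, additive score. Let B be irritation already present, N and C the irritation added by the novel and conventional sockets, and r the fraction of the first socket's effect still visible after the second.

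- Novel first: the reports are B + N, then B + rN + C. Novel minus conventional = N − C − rN.
- Conventional first: the reports are B + C, then B + rC + N. Novel minus conventional = N − C + rC.
- B cancels in both orders, so a stable lesion does not remove the socket comparison.
- With equal numbers in each order, the average is (N − C) + r(C − N)/2 = (N − C)(1 − r/2). Carry-over shrinks the difference towards none, by an amount the plan cannot estimate.
- N and C are not separately identifiable, because B is never observed.
- With an inspection before each socket, B and B + rN (or B + rC) are observed. Subtracting them from the matching reports gives N and C directly.

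**3. How many subjects might be affected?** The inputs are 18 subjects (protocol section III) and an assumed prevalence p. Expected number = 18p; chance of at least one = 1 − (1 − p)^18.

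| Assumed p | Expected among 18 | Chance of at least one |
|---|---|---|
| 5% | 0.9 | 60.3% |
| 10% | 1.8 | 85.0% |
| 20% | 3.6 | 98.2% |
| 30% | 5.4 | 99.8% |

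These values are illustrative only. They make no allowance for the comfortable-socket and general-health requirements, which probably lower p.

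**4. Would a skin criterion cost the trial its power?** Section III states that 12 subjects are needed to detect 10% of 97 kPa (9.7 kPa) with SD 8.9 kPa, two-sided 0.05 and 90% power. Taking 8.9 as the SD of the paired difference, the standardised effect is 9.7/8.9 = 1.09. The exact paired t-test first reaches 90% at 11 subjects (90.2%) and gives 92.9% at 12, close to the stated number. If affected subjects were left out and not replaced, power for contact pressure would be 98.2% with 16 subjects, 96.4% with 14, 92.9% with 12 and 86.5% with 10. At assumed prevalences up to 30%, the expected number left is at least 18 − 5.4 = 12.6, so the protocol's own target would on average still be met.

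**The case against.** The case against has real weight.

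- **The design protects the comparison.** Each subject wears both sockets in random order with a report after each. A reader might infer that the skin result of someone with an existing lesion tells us nothing about the socket. The documents do not support that. A written report can record worsening or a new site, and a stable lesion cancels in the difference. The stronger reading would need reports reduced to present or absent for the whole limb, and nothing says they are.
- **No interval is planned for skin.** A reader might also infer that affected pairs widen the confidence interval by a calculable amount. Irritation is not among the measurements listed in section III or the SAP, so there is no interval to widen. Pairs kept with a zero difference also behave differently from pairs that are dropped.
- **Indirect filters exist.** A person with an open lesion may not be judged healthy or comfortable in the current socket. That lowers the likely number but does not close the gap, since the prosthetist's judgement is of the socket.
- **Clinicians are present in Session 2.** The limb is bared for sensor placement before loading, both clinicians attend fitting, and the subject may stop at any time. This is a genuine safeguard for that session. It produces no baseline record and does not extend to the Session 1 indentation, although that testing is non-invasive.
- **The first report partly serves as a baseline for the second socket.** This is true, but the plan does not say it will be used so, and the first-worn socket has no baseline at all.

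**Conclusion.** The point stands as a gap in screening and attribution. The protocol has no residual-limb skin criterion, and the only described inspection follows socket wear. A limb with an existing lesion could therefore be indented, taped and loaded, and the irritation found afterwards could not be assigned to the socket just worn. The comparison between sockets is weakened but remains informative.

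Its size cannot be fixed from the documents. The 5% to 30% range, giving 0.9 to 5.4 of 18 subjects, is an assumption and not an estimate for these selected participants. The carry-over result rests on an additive score and equal numbers in each order, neither of which the protocol specifies. The conclusion rests on the protocol's eligibility, methods and risk text and on the SAP's statistical analysis section. It is a cheap improvement worth making before enrolment, and does not undermine the other outcomes.

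**What to change.** 1. In protocol section III, Inclusion and exclusion criteria, add a criterion on the skin of the residual limb. The study dermatologist should set its content, and study staff should confirm it before the Session 1 indentation.
2. In section V, Session 2, have the dermatologist inspect and record the skin before sensors are applied for the first socket, and again before the second.
3. State that irritation after each socket will be interpreted as change from the inspection immediately before it.

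**Cost.** One eligibility line, a few extra minutes per session and an occasional rebooked visit. The dermatologist is already due to attend Session 2; only the Session 1 check has to be arranged.

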In pursuit of our long-term goal, our team has recently developed a framework for prosthetic socket design and fabrication that involves: 1) non-invasive imaging to record patient geometry, 2) indentation to assess tissue mechanical properties, 3) data-driven and automated creation of patient-specific designs, 4) patient-specific finite element analysis and design evaluation, and 5) 3D printing of the end design for clinical evaluation. This study aims to advance these approaches, and clinically assess the overall design process for N=18 transtibial amputees. Socket evaluations are conducted during standing and walking activities. For these evaluations, skin-socket interface pressures are recorded using sensors located at the skin-socket interface. During the walking evaluation, motion capture is used additionally to allow for gait analysis. Furthermore, metabolic cost is measured by indirect calorimetry using an open circuit respirometry system. These experiments are repeated for each patient's conventional socket for comparison. In addition to these quantitative evaluations, each study participant completes a socket evaluation questionnaire, and a certified dermatologist writes a report documenting skin conditions subsequent to each socket test.

The main hypothesis of this proposal is that the novel quantitative socket is equivalent to, or better than, a conventional socket in terms of: 1) skin contact pressures, 2) gait symmetry, 3) walking metabolic cost, 4) skin irritation levels as assessed by the dermatologist, and 5) comfort as evaluated from a questionnaire. Furthermore, we hypothesize that equivalence or improved socket performance can be achieved for all N=18 subjects using a single computational design framework, i.e. that we can formulate the computational design framework such that it can automatically design these sockets for all subjects without requiring algorithm adjustments from one subject to the next.

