During a second session the sockets (designed based on the image and mechanical property data) are evaluated (at the MIT Media Lab's Biomechanics department). In this session both the conventional and novel socket systems will be tested. For all subjects the order of testing (conventional or novel first) is randomized. Subjects are first asked to sit on a chair and expose their residual limb surface for force sensor placement. Recently we established a new inter-socket skin contact pressure assessment system based on flexible pressure and force sensors (A201, 111N, FlexiForce®, TekScan, Boston, MA, USA, and also F-Socket, TekScan, Boston, MA, USA). Data for an array of force sensors can be simultaneously recorded during static standing or dynamic walking exercises. Evaluating loads at select anatomical regions are of interest, these sites include: 1) the medial crest, 2) the fibular head, 3) the tibial crest, and 4) the Mid posterior wall. Sensors are secured to the skin using a thin adhesive tape (12.7 mm wide, 0.0625 mm thick, Scotch Magic®, 3M, USA) which can be removed with minimal discomfort. After sensor placement a liner is rolled over the skin and sensors. The conventional sockets are evaluated with the subject's own liner and suspension system. For evaluation with the novel socket, subjects are fitted with a custom liner (e.g. through Ottobock Healthcare GmbH) or standard commercially available liners (such as the Silosheath Double cushion 3-mm liner, Silipos Holding LLC, Niagara Falls, N.Y, USA). A commercially available sleeve is used for suspension (such as BK Suspension sleeve, Silipos Holding LLC, Niagara Falls, N.Y, USA). Next the compliant socket and rigid outer socket are donned on. For the novel sockets the outer socket is first attached to the subject's conventional foot-ankle system, and alignment is optimized by a certified prosthetists (present during all socket fitting and evaluation procedures) consulted for this study ([name], A Step Ahead Prosthetics). Once subjects have been fitted with the sockets the standing, followed by the walking exercise is conducted. For the walking exercise not only force but also metabolic cost and motion capture data are recorded. The metabolic analysis will provide an assessment of the energy expenditure while wearing either a conventional or the novel socket (discomfort may result in a less efficient or asymmetric gait causing increased energy use). For metabolic cost analysis, subjects are equipped with a breath-by-breath portable telemetric system (Model K4b², COSMED, Rome, Italy). Subjects are also equipped with 46 reflective markers (15 mm diameter) for motion capture (following the Helen Hayes marker model). For the standing evaluation subjects are asked to stand still in an upright position for 5 minutes while skin contact force (or pressure) data and resting state metabolic data is acquired.

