
For the walking evaluation subjects are asked to walk at 1.4 m/s for 10 minutes on an instrumented treadmill (Bertec, Columbus, OH) while ground reaction forces are recorded, as well as 3D marker locations and the metabolic data. The marker locations are recorded at a sampling rate of 100 Hz by a 12 infrared camera motion capture system (model: T40s, Vicon Motion Systems Ltd, Oxford, UK). The locations of these markers is chosen to track joint motion.

The treadmill system used for the walking exercise is equipped with parallel bars to prevent any injury to the subject if he were to lose balance and fall. A safety harness attached to the ceiling will also be utilized if the subject makes that request. In addition, a member of the laboratory staff will also accompany the study participant to catch him/her in the event of a fall, if necessary. The participant may ask to rest or to terminate their participation in the study at any time. The socket evaluation session (walking and standing evaluations) should take no more than 4 hours to complete.

The kinematic and force plate data can be combined with inverse dynamics analysis to compute joint angles and moment profiles. Furthermore, analysis between data for the left and right limb and for the conventional and novel socket allows for comparison of symmetry measures. Symmetry indices will be derived for: 1) ankle, knee, and hip joint angle, position, torque time profiles, and 2) the vertical ground reaction forces. The metabolic measurements for standing will be

subtracted from the metabolic rate of walking trials in order to obtain the net metabolic cost of walking.

After the standing and walking exercises subjects will be requested to take off the socket and liner to expose their residual limb skin surface. The consultant dermatologist ([name]) will then inspect the skin and report on skin irritation. The dermatologist will also talk to the subjects on comfort and instruct them to fill out the developed socket evaluation questionnaire. Questions will also relate to points where contact pressure measurements will be made, thus enabling direct comparison of local comfort assessment to pressure findings. Subjects fill out their answers by drawing a line at a desired level for each of the questions. This method allows for post-processing based conversion of the input to numerical data (i.e. 0-100 %) and lacks biases associated with constrained integer number input (e.g. favoring of even/odd numbers).

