Data & Safety Monitoring Plan

All sensor (e.g. force/pressure) data is recorded using data acquisition units (e.g. Arduino Uno, Arduino LLC) connected to dedicated laptop computers. The motion capture data (VICON system) and treadmill data (speed and force plates) are recorded using a dedicated desktop computer. The metabolic cost analysis are recorded on a dedicated data acquisition unit (COSMED) and are subsequently uploaded to a laptop computer.

We will record video (in digital format) for each subject walking for analysis and development purposes. Videos in digital format will be archived in a password protected secure server located at the MIT Media Laboratory. Access to video material will be limited to authorized investigators associated with this study. Video will remain archived in the data server for future reference. Upon subject request, videos can be deleted from server once study is completed.

Benefits

There are no immediate benefits for participating in this study. The prosthetic sockets produced will be prototypes and would not be immediately available.

It is expected that knowledge generated in this study will benefit society. The processes developed for producing 3D printed sockets during this research will be used to understand how to most effectively attach (mechanical) devices to humans. This understanding will aid the development of advanced prostheses, orthoses and other augmentation/rehabilitation technologies.

Risks

Following the inclusion criteria (which include MRI safety) there should be no elevated risk associated with the MRI acquisitions. Other risks and discomforts are minimal as they are those incurred by standing still for 5 minutes, and walking on a treadmill for 10 minutes, both while using either a conventional socket and the 3D printed socket.

There will be a "spotter" standing next to the treadmill and close to the amputee while standing or walking in our facilities. We will give subjects periodic rest/water breaks. Any other necessary assistance to make the subjects comfortable will be provided. If during the standing or walking exercise the subject experiences discomfort such that he/she wishes to terminate the test he/she can decide to do so at any time. To minimize these uncomfortable situations, we will have a certified prosthetist and a dermatologist around during the fitting process during the socket evaluation.

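### Both sockets are tested on the same limb in one session with no set interval and no pre-socket skin or comfort reading, so readings after the second socket can include residue from the first

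*Protocol*

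**What the plan says.** Protocol section V, Session 2 (phase 3), sets the design: "In this session both the conventional and novel socket systems will be tested". Order is handled by randomisation: "For all subjects the order of testing (conventional or novel first) is randomized". With each socket the subject is asked to "stand still in an upright position for 5 minutes" and then to "walk at 1.4 m/s for 10 minutes on an instrumented treadmill". The whole visit is capped: "The socket evaluation session (walking and standing evaluations) should take no more than 4 hours to complete".

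Skin is assessed afterwards: section V (Methods) says that "a certified dermatologist writes a report documenting skin conditions subsequent to each socket test". Session 2 adds that, once the exercises are done, the socket and liner come off, the dermatologist inspects the limb, and the subject completes a line-marking questionnaire that is converted to 0–100%. I read the questionnaire as completed once per socket, since a paired comparison needs that.

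Two provisions for rest appear. Under Risks: "We will give subjects periodic rest/water breaks". In Session 2: "The participant may ask to rest or to terminate their participation in the study at any time". Neither is placed between the sockets, given a length or linked to the state of the limb. No skin or comfort reading before either socket is described.

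Protocol section III and the SAP's statistical analysis section compare the sockets by paired t-test for scalars and ANOVA for time series. Neither mentions carryover.

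**The concern.** This is a two-period crossover on one residual limb within a few hours. Redness, tenderness or tissue change from the first socket may still be present when the second is donned. Without a reading at that moment, the second skin report and the second questionnaire cannot separate new irritation from old.

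Skin irritation and comfort are two of the five components of the main hypothesis, which is that the novel socket is at least as good as the conventional one. No margin is stated for any component. A difference that has been diluted could therefore be read as support, and one that has been inflated or created could be read as a finding.

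**Working it through.** **The plan's own figure.** The only sample-size figure is for pressure. The inputs are mean 97 kPa, SD 8.9 kPa, a 10% difference (9.7 kPa), two-tailed 0.05 and 90% power (Protocol III, Sample Size). With d = 9.7/8.9 = 1.09, the paired t-test needs 11 subjects (power 90.2%), and 12 gives 92.9%. The stated 12 is therefore reproduced to within one subject, if 8.9 kPa is taken as the SD of paired differences, which the protocol does not say. Neither document gives a figure for carryover, so what follows is algebra plus assumed ranges.

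**Model.** Let N and C be the true mean scores for the novel and conventional socket, with higher meaning worse. Let c_N and c_C be the residue each leaves on the next reading, and p a shift common to all second tests. Half the subjects take each order.

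- Novel mean = (N + N + p + c_C)/2 = N + p/2 + c_C/2
- Conventional mean = (C + C + p + c_N)/2 = C + p/2 + c_N/2
- Difference = (N − C) + (c_C − c_N)/2

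The common shift p cancels. The differential residue does not, and an order term in the model would not remove it either. Under simple randomisation p cancels only on average. No blocking is stated, and the chance that 18 subjects split 12:6 or worse is 24%.

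**Case 1: both sockets leave the same share L.** Then c_N = L·N and c_C = L·C, and the difference is (N − C)(1 − L/2). For illustrative discomfort scores N = 30 and C = 20 (true difference +10):

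| L (assumed) | Expected difference | Shrinkage |
|---|---|---|
| 10% | 9.5 | 5% |
| 20% | 9.0 | 10% |
| 30% | 8.5 | 15% |
| 50% | 7.5 | 25% |

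**Case 2: the shares differ.** The difference is N(1 − L_N/2) − C(1 − L_C/2).

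- N = 30, C = 20, L_N = 0.1, L_C = 0.5: 30 × 0.95 − 20 × 0.75 = 28.5 − 15 = +13.5. A true +10 is enlarged.
- N = C = 20, L_N = 0.1, L_C = 0.3: 20 × 0.95 − 20 × 0.85 = 19 − 17 = +2. A difference is created from none.

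The bias opposes the true difference when the worse socket leaves more behind (c_N > c_C when N > C). It reinforces the difference when the better socket leaves more behind.

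**Could the analysis detect it?** Hardly. As an illustration, take a carryover of 4.85 kPa against an SD of 8.9 kPa (4.85/8.9 = 0.54 SD). A comparison of the two orders, 9 against 9, at alpha 0.10 has about 16% to 18% power for within-subject correlations of 0.7 to 0.3 (assumed).

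**Time available.** Recorded exercise is 2 × (5 + 10) = 30 minutes of 240, or 12.5%. Sensor placement, 46 markers, fitting, alignment, skin inspection and questionnaires must also fit within the 4 hours, so there may be room for an interval, but the documents do not show how much.

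**The case against.** The strongest points on the other side are these.

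- **Some interval exists already.** The socket and liner come off for inspection and the questionnaire, and the subject's foot-ankle unit is attached to the novel socket, so hardware has to change over. This stands, but its length is not controlled and nothing is recorded at its end.
- **Exposure is short and the subjects are robust.** There are 15 minutes of recorded exercise per socket, in subjects of at least K3 activity, more than a year after amputation, whose own sockets are judged comfortable. This makes large carryover less likely but does not exclude it.
- **Part of the residue cancels.** Sensors are taped at the same named sites whichever socket is worn, so tape marks are largely a common shift. This stands.
- **The additive model does not suit pressure.** Pressure is recorded live under the worn socket. Adding 50% of a 97 kPa reading would raise the next one by 48.5 kPa, which is not credible. Carryover into pressure would need a change in limb volume or tissue, and the documents give neither its sign nor its size. Even if Case 1 is applied to pressure, L of 10% to 50% lowers power at N = 18 only from 99.2% to between 98.5% and 90.4%. This stands; skin and comfort are the concern.
- **Skin has no planned test.** No skin score is defined, and skin is absent from the list of analysed measurements. The algebra therefore applies most directly to the questionnaire; for skin the problem is one of interpreting the second report.

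A reader might infer that carryover always pulls the result towards no difference and so always favours an equivalence claim. The documents do not support that. It requires the worse socket to leave more behind, and the two sockets are worn with different liners and suspension, so equal shares cannot be presumed. Shrinkage also favours equivalence only if a non-significant result is read that way, which is a separate weakness arising from the missing margin.

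**Conclusion.** The concern holds for skin irritation and comfort. As written, readings after the second socket can include residue from the first, and the plan has no means of recognising it. Randomised order deals with a common second-test shift on average but leaves a bias of (c_C − c_N)/2. If a common share L persists, the difference shrinks by L/2, or 5% to 25% for L of 10% to 50%. With unequal shares the bias can go either way.

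These sizes rest on an assumed L and a balanced order. The documents do not establish that carryover occurs, and for pressure it is less certain. This is a worthwhile, inexpensive improvement to the design, not a defect that invalidates the trial.

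**What to change.** In Protocol section V, Session 2:

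1. Add a socket-off interval between the two tests, with a fixed minimum length set by the investigators and the same in both orders.
2. Immediately before each socket is donned, have the dermatologist, who is already present, record skin condition at the sensor sites, and have the subject complete the comfort scale.
3. Assess skin and comfort for each socket relative to its own pre-socket reading, and report any subject whose skin had not returned to its state before the first socket.
4. If a comparison using only each subject's first socket is shown, label it a low-power sensitivity check. It is unpaired; at 9 against 9, with 9.7/8.9 kPa and 8.9 taken as the between-subject SD, power is about 58%.

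Step 3 has a limit. If a share f of the residue present at donning remains at the end of the second test, the raw bias is f(c_C − c_N)/2 and the bias after subtraction is −(1 − f)(c_C − c_N)/2. Subtraction is exact only at f = 1 and reduces the bias only when f exceeds one half. The interval in step 1 is therefore the main protection, and raw post-test scores should be reported alongside.

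Cost: protocol wording, a somewhat longer session, and one extra short reading per socket by staff already in the room.
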